1. SYNOPSIS

Vanda Pharmaceuticals Inc.

Name of Investigational Product:

tradipitant (VLY-686)

Title of Study:

A Randomized, Double-Blind, Placebo-Controlled, Efficacy Study of the Neurokinin-1 Receptor Antagonist VLY-686 in Patients with Atopic Dermatitis

Study Center(s): Multicenter in the United States

Studied Period: Phase of Development:

Date first patient enrolled: October 2019

Estimated study duration: 1 year

III

Number of Patients (planned):

Approximately 200 patients randomized (100 per arm, 1:1 randomization scheme), diagnosed with mild atopic dermatitis with treatment-resistant pruritus (i.e., pruritus duration of at least 6 weeks despite the use of antihistamines or corticosteroids).

Inclusion Criteria:

- 1. Ability and acceptance to provide written informed consent; and sufficiently fluent in English to participate in the trial;
- 2. Male and non-pregnant, non-lactating female patients aged 18 70 years (inclusive);
 - a. Note: Principal investigators are advised to enroll a patient population that reflects the demographics of the overarching United States population. Demographics in this context refer to age, sex, race, and ethnicity.
- 3. Diagnosed with atopic dermatitis:
 - a. $\geq 1\%$ body surface area (BSA) of AD involvement at the screening and baseline visits;
 - b. Validated Investigator Global Assessment scale for Atopic Dermatitis (vIGA-AD) rating of 1 or 2;
 - c. Presence of excoriations at screening and baseline visits (i.e., SCORing Atopic Dermatitis index excoriation score > 0).
- 4. Suffering from chronic pruritus with pruritus being actively present for at least 6 weeks prior to screening despite the use of antihistamines or corticosteroids;
- 5. Worst Itch Numerical Rating Scale (WI-NRS) score ≥ 5 points at the screening and baseline visit:
- 6. Daily diary reporting Worst Itch Numerical Rating Score (WI-NRS) average score for maximum itch severity ≥ 7 points between screening and baseline visits;

- a. Note: WI-NRS average score for maximum itch severity will be determined based on the average of the 50% worst daily NRS scores for maximum itch severity (the daily scores ranging from 0 to 10) during the screening period (between visits 1 and 2). A minimum diary compliance of 70% during the screening phase (between Visits 1 and 2) is required before randomization. For patients who do not have at least 70% diary compliance preceding the planned randomization date, randomization should be postponed until this requirement is met, but without exceeding the 45-day maximum duration for screening.
- 7. Patients with Body Mass Index (BMI) of ≥ 18 and $\leq 40 \text{ kg/m}^2$ (BMI = weight (kg)/ [height (m)]²);
- 8. Patients must agree to the following study restrictions:
 - a. Males of procreative capacity (not surgically sterile) will use an acceptable method of contraception from randomization through 1 month following the last dose of study medication. Examples of acceptable contraception for males include abstinence, use of a barrier method, or surgically sterilized or post-menopausal partner.
 - b. Females of childbearing potential (not surgically sterile or post-menopausal, defined as 12 months with no menses without a medical cause) will use an acceptable method of contraception from the screening visit or 1 month prior to randomization, whichever is earlier, through 1 month after the last dose of study medication. Examples of acceptable methods of contraception for females include abstinence, the use of 2 independent barrier methods, hormonal contraception plus 1 barrier method, or surgically sterilized partner.
- 9. Willing and able to comply with all study requirements and restrictions;
- 10. Willing to not participate in any other interventional trial for the duration of their participation;
- 11. Patients must be in good health as determined by past medical history, physical examination, electrocardiogram, clinical laboratory tests, and vital signs.

Exclusion Criteria:

- 1. Chronic pruritus due to condition other than atopic dermatitis (AD);
- 2. Superinfection of AD;
- 3. Unwilling or unable to follow medication restrictions described in Section 9.2, or unwilling or unable to sufficiently washout from use of restricted medication;
- 4. Under medical treatment for a skin disease with a therapy listed in the prohibited medications section in Table 3 that may influence the results of the study;
- 5. Have been treated with the following therapies:
 - a. An investigational drug, including placebo, within 8 weeks or within 5 half-lives (if-known), whichever is longer, prior to the baseline visit or
 - b. An AD or immune-related biologic for less than 5 half-lives (if known) or 16 weeks prior to the baseline visit.

- c. Note: For clarity, an example of such biologics would be drugs such as dupilumab (approved by the FDA for treatment of AD) and fezakinumab (a biologic being investigated in AD).
- 6. Recent history (within six months of screening) of drug or alcohol abuse as defined in DSM-5 Diagnostic Criteria for Drug and Alcohol Abuse and/or a positive drug or alcohol screen at the Screening visit;
- 7. Patient has made a suicide attempt and/or had suicidal ideation of type 4 or 5 on the Columbia-Suicide Severity Rating Scale (C-SSRS) in the past 2 years, or patient is at risk of suicide at Screening or Baseline, in the opinion of the Investigator;
- 8. Any medical procedure requiring general anesthetic within three months of the Baseline Visit or any procedure requiring sedation within one month of the baseline visit;
- 9. Current clinically significant cardiovascular, respiratory, neurologic, hepatic, hematopoietic, renal, gastrointestinal, or metabolic dysfunction unless currently controlled and stable, including (but not limited to) the following:
 - a. Uncontrolled diabetes mellitus defined as HbA1c > 7%;
 - b. Positive hepatitis C antibody test (anti-HCF);
 - c. Positive hepatitis B surface antigen (HBsAg).
- 10. History (including family history) or current evidence of congenital long QT syndrome or known acquired QT interval prolongation;
- 11. History of intolerance and/or hypersensitivity to medications similar to tradipitant and its accompanying excipients;
- 12. Indication of impaired liver function (values for AST, ALT, or bilirubin > 2 times the Upper Limit of Normal (ULN));
- 13. Has a creatinine level > 1.25x ULN;
- 14. Randomization in a previous tradipitant clinical trial;
- 15. Anyone affiliated with the site or sponsor and/or anyone who may consent under duress;
- 16. Any other sound medical reason as determined by the Investigator including any condition which may lead to an unfavorable risk-benefit of study participation, may interfere with study compliance or may confound study results.

Investigational Product, Dosage, and Mode of Administration:

A single oral capsule of tradipitant 85 mg or matching placebo will be orally administered twice daily for a total daily dose of 170 mg.

Duration of Treatment (Randomization Phase):

8 weeks

Reference Therapy, Dosage, and Mode of Administration:

Placebo capsules will be provided in size and appearance identical to those containing VLY-686 and will be orally administered twice daily.

Objectives:

Primary Objective:

• To evaluate the efficacy of VLY-686 in reducing worst itch in patients with chronic pruritus in atopic dermatitis as measured by Worst Itch Numerical Rating Scale (WINRS) at Week 2.

Secondary Objectives:

- To evaluate the efficacy of VLY-686 in reducing sleep disruption as measured by daily diary sleep scale (DDSS).
- To evaluate the efficacy of VLY-686 in improving disease severity in patients with atopic dermatitis as measured by the validated Investigator Global Assessment scale for Atopic Dermatitis (vIGA-AD).
- To evaluate the efficacy of VLY-686 in improving disease severity in patients with atopic dermatitis as measured by the SCORing Atopic Dermatitis (SCORAD) index and Eczema Area and Severity Index (EASI).
- To evaluate the proportion of patients with improvement on SCORAD index of at least 50%, 75%, or 90% improvement.
- To evaluate the proportion of patients with improvement on the EASI of at least 50%, 75%, or 90% improvement.
- To assess the efficacy of tradipitant on global measures of improvement as measured by Clinical Global Impression of Change (CGI-C) and Patient Global Impression of Change (PGI-C).
- To assess the efficacy of tradipitant on quality of life as measured by the Patient Oriented Eczema Measure (POEM), Dermatology Life Quality Index (DLQI), Healthy Days Core Module (4 questions) (HRQOL-4), Insomnia Symptom Questionnaire (ISQ), and Patient Benefit Index Pruritus (PBI-P).
- To explore the safety and tolerability of multiple oral doses of VLY-686.

Pharmacogenomic Sub-Study:

- Identify genetic markers that correlate with response to tradipitant treatment.
- Identify genetic markers that correlate with adverse events that may occur upon treatment with tradipitant.
- To identify genetic markers that are associated with atopic dermatitis and/or pruritus and disorders/diseases associated with NK-1 receptors.
- To identify genetic markers that are associated in the metabolism, distribution, and/or excretion of tradipitant and its metabolites.

Overall Design:

This is multicenter, randomized, double-blind, placebo-controlled study to be conducted in the United States. Approximately Two Hundred (200) patients diagnosed with mild atopic dermatitis, who satisfy the eligibility criteria for the study, will be randomized to receive either tradipitant 85 mg or matching placebo BID.

The study is divided into two phases: the pre-treatment phase and the evaluation phase. The pre-treatment phase includes a screening and a baseline visit where patients' eligibility for the study will be assessed. Washout of medications will occur during the screening phase.

The evaluation phase includes 8 weeks of randomized, double-blind, placebo-controlled treatment. In-clinic evaluations will occur at Screening, Baseline, and Weeks 2, 4, 6, and 8.

Criteria for Evaluation:

Efficacy:

Efficacy assessments will include:

- Worst Itch Numerical Rating Scale (WI-NRS)
- SCORing Atopic Dermatitis (SCORAD) index
- Validated Investigator Global Assessment scale for Atopic Dermatitis (vIGA-AD)
- Eczema Area and Severity Index (EASI)
- Clinical Global Impression of Change (CGI-C)
- Patient Global Impression of Change (PGI-C)
- Patient Oriented Eczema Measure (POEM)
- Dermatology Life Quality Index (DLQI)
- Patient Benefit Index Pruritus (PBI-P)
- Insomnia Symptom Questionnaire (ISQ)
- Healthy Days Core Module (4 questions) (HRQOL-4)

Safety:

- Safety and tolerability assessments will include the recording of adverse events (AEs), physical examinations, clinical laboratory assessments, vital signs, and electrocardiograms.
- The Columbia-Suicide Severity Scale (C-SSRS) will be used to assess suicidal behavior and ideation.

Table 1: Schedule of Evaluations

Phase	Pre-Tre	Pre-Treatment		Evaluation				
Visit	V1 Screening	V2 Baseline	V3	V4	V5	V6		
Study Day	Up to Day -45	Day 0	Day 14 ¹	Day 28 ¹	Day 42 ¹	Day 56 ¹ or ET		
Informed Consent Form (ICF) ²	X							
Eligibility assessment	X	X						
Patient demography	X							
Medical history	X							
Prior/concomitant medications	X	X	X	X	X	X		
Adverse Event (AE) Assessment ³	X	X	X	X	X	X		
Serum β-HCG (for WOCBP)	X					X		
Urine pregnancy test (for WOCBP)		X	X	X	X			
HbA1c	X							
Hepatitis B/C screen	X							
Drug and alcohol screen	X	X	X	X	X	X		
Hematology, chemistry, and urinalysis ⁴	X	X	X	X		X		
Coagulation ⁴	X							
IgE collection	X	X	X	X	X	X		
Cytokine Panel ⁵	X					X		
Filaggrin Analysis ⁶	X							
Pharmacogenetic (PG) sample ⁶	X							
Pharmacokinetic (PK) sample		X	X	X	X	X		
Resting 12-lead ECG	X	X	X	X	X	X		
Vital signs and body measurements ⁷	X	X	X	X	X	X		
Physical Examination (PE) ⁸	X	X	X	X	X	X		
Columbia-Suicide Severity Rating Scale (C-SSRS) ⁹	X	X	X	X	X	X		
Medical History of Pruritus Questionnaire		X						
Medical History of Atopy Questionnaire	X							
Pruritus Assessment (incl. NRS, VRS)	X	X	X	X	X	X		
SCORing Atopic Dermatitis (SCORAD) index	X	X	X	X	X	X		
Eczema Area and Severity Index (EASI)	X	X	X	X	X	X		
Validated Investigator Global Assessment scale for Atopic Dermatitis (vIGA-AD)	X	X	X	X	X	X		
Patient Benefit Index – Pruritus (PBI-P) ¹⁰		X	X	X	X	X		

Phase	Pre-Treatment		Evaluation			
Visit	V1 Screening	V2 Baseline	V3	V4	V5	V6
Study Day	Up to Day -45	Day 0	Day 14 ¹	Day 28 ¹	Day 42 ¹	Day 56 ¹ or ET
Patient Global Impression of Change (PGI-C)			X	X	X	X
Clinical Global Impression of Change (CGI-C)			X	X	X	X
Patient Oriented Eczema Measure (POEM)	X	X		X		X
Dermatology Life Quality Index (DLQI)	X	X	X	X	X	X
Insomnia Symptom Questionnaire (ISQ)	X	X		X		X
Healthy Days Core Module (4 questions) (HRQOL-4)	X	X		X		X
Daily Diary	←					*
Photography		X		X		X
Randomization		X				
Study medication dispensation ¹¹		X	X	X	X	
Study medication collection & compliance			X	X	X	X
Daily diary distribution and instruction	X					
Patient daily diary review		X	X	X	X	X

- 1 Within +/- 3 days.
- 2 Informed Consent will be obtained prior to performance of any study procedure(s).
- 3 Adverse Event collection will begin at the time the ICF is signed.
- 4 If elevated liver enzymes are present at any study visit, an unscheduled visit to redraw chemistry and coagulation samples will be completed prior to the next scheduled visit.
- 5 If the V1 cytokine panel sample is missed, the sample should be drawn at the next in-clinic visit (ex. V2).
- 6 If either the V1 Filaggrin or PG sample is missed or unable to be performed for any reason, the samples should be drawn at the next in-clinic visit (ex. V2).
- 7 Body height will only be collected at V1; body weight will be collected at V1, V2, and V6.
- 8 An abbreviated physical examination will be performed at V2-V5 ONLY if clinically indicated.
- 9 The Baseline C-SSRS will occur at V1. The Since Last Visit C-SSRS will occur at all other visits.
- 10 At V2, the Patient Needs Questionnaire (PBI-P(PNQ)) will be administered. The Patient Benefits Questionnaire (PBI-P(PBQ)) will be administered at subsequent visits.
- 11 Patients will be instructed to take their first dose of study medication on the evening of Day 0 (V2).

ET = Early Termination; WOCBP = Women of Child-bearing Potential; ECG = Electrocardiogram; C-SSRS = Columbia Suicide Severity Rating Scale; NRS = Numeric Rating Scale; VRS = Verbal Response Scale; HbA1c= Haemoglobin A1c or glycated haemoglobin; IgE= Immunoglobulin E

1. STATISTICS

1.1. Sample Size and Accrual

A total sample size of 200 patients (100 per arm) will provide approximately 93% power to detect a 25% response rate difference, assuming 30% and 55% response rates in placebo and VLY-686 treatment groups respectively, based on a two-sided Fisher's Exact Test with a 5% significance level. In addition, 200 patients will provide about 90% power to detect a 1.2-point treatment difference in worst itch score, as measured by WI-NRS, between VLY-686 and placebo with a standard deviation (SD) of 2.6, based on a two-sided Student's T-Test with a 5% significance level.

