1.2.2. Patient Populations for Analysis

The following analysis populations will be defined for this study:

Intent-to-Treat: Any patient randomized into the study that receives a dose of study drug and that has completed at least one post-baseline efficacy measurement while on study medication;

Safety: Any patient randomized into the study that receives a dose of study drug;

Per-Protocol: Any patient who is randomized and receives the protocol required study drug exposure and required protocol processing.

Efficacy analyses will be performed on the Intent-to-Treat population and the Per-Protocol population. Safety summaries will be based on Safety set. Patient characteristics will be presented for all patients randomized.

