1.3. Efficacy Data Analysis

1.3.1. Primary Outcome and Methodology

The primary efficacy outcome measure for the double-blind phase will be the WI-NRS responder rate at Week 2. A WI-NRS (worst itch numerical rating scale) responder is defined as a patient achieving at least 4 points reduction from baseline in WI-NRS. The primary statistical method will be the CMH (Cochran–Mantel–Haenszel) test. A detailed description of the primary analysis model and the corresponding sensitivity analysis will be included in the SAP.

As stated previously, any changes in the statistical methods that occur prior to database lock will be documented in the SAP and will not require a protocol amendment.

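### Do the two power figures in the sample-size section assume different treatment effects, leaving the primary responder test short of its stated power?

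*SAP*

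**What the plan says.** SAP Section 1.1 (Sample Size and Accrual) makes two statements about the same 200 patients.

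- **Responder rate:** "A total sample size of 200 patients (100 per arm) will provide approximately 93% power", "assuming 30% and 55% response rates in placebo and VLY-686 treatment groups respectively", "based on a two-sided Fisher's Exact Test with a 5% significance level".
- **Continuous score:** the same number gives "about 90% power to detect a 1.2-point treatment difference in worst itch score", with SD 2.6 and a two-sided 5% t-test. The visit is not named, and the section does not say whether 2.6 is the SD of the score or of its change.

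SAP Section 1.3.1 sets the primary outcome as the WI-NRS responder rate at Week 2, tested by CMH. A responder is "a patient achieving at least 4 points reduction from baseline in WI-NRS". Continuous WI-NRS is a secondary outcome in Section 1.3.2, analysed by MMRM.

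The Protocol Synopsis plans "Approximately 200 patients randomized (100 per arm, 1:1 randomization scheme"), the same count that both power statements use. The intent-to-treat set in SAP Section 1.2.2 keeps dosed patients only if each is one "that has completed at least one post-baseline efficacy measurement while on study medication". No dropout rate is given.

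**The concern.** The primary endpoint dichotomises the scale on which the 1.2 points are measured, so a difference in means and a difference in response rates are not free of each other. A reader who takes the paragraph as one planning scenario will conclude that 200 patients give at least 90% power on both measures for one drug effect. Under a simple normal model they do not: the responder assumption needs an effect about 40% larger than 1.2 points. If 1.2 points were the true effect, the chance of missing the primary endpoint would be about 33% (Fisher) or 28% (CMH) instead of the roughly 7% stated, and the trial could succeed on the continuous score while failing its primary test. Counting all 200 randomised patients as analysed adds some further optimism.

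**Working it through.** **Inputs from the documents:** 100 per arm; 30% and 55% response; 1.2 points; SD 2.6; two-sided 5% tests; response threshold of 4 points.

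**Assumptions that the documents do not supply:** change scores normal with equal SD in both arms; 2.6 is the SD of change at Week 2; placebo response is 30% in the 1.2-point case.

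**1. The plan's own figures.**
- Exact enumeration of the two-sided Fisher test, 100 per arm, 0.30 against 0.55: power 93.9% (stated: about 93%). The unstratified CMH test gives 95.5%.
- t-test: noncentrality = 1.2 / (2.6 × √(2/100)) = 1.2 / 0.3677 = 3.26 on 198 df; power 90.1% (stated: about 90%).

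Both reproduce.

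**2. Linking the scales under the normal model.**
- Shift implied by 30% to 55%: Φ⁻¹(0.55) − Φ⁻¹(0.30) = 0.650 SD; 0.650 × 2.6 = 1.69 points; 1.69 / 1.2 = 1.41.
- Response implied by 1.2 points: Φ(Φ⁻¹(0.30) + 1.2/2.6) = 0.475, a difference of 17.5 percentage points.
- Power at 0.30 against 0.475, 100 per arm: Fisher 67.4%, CMH 72.4%.

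**3. How far this depends on the assumptions.**

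| Assumption (1.2-point shift, 30% placebo response) | Fisher | CMH |
|---|---|---|
| Normal, SD 2.6 | 67% | 72% |
| Integer scores bounded at 0–10, SD 2.6 | 68–70% | 73–74% |
| Logistic shape, SD 2.6 | 78% | 82% |
| All shapes tried at SD 2.6 (including heavy-tailed and skewed) | 63–90% | – |
| Normal, SD of change 2.2 | 83% | 86% |
| Normal, SD of change 3.0 | 54% | 60% |

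Under normality the scenarios agree exactly when the SD is 1.2 / 0.650 = 1.85.

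**4. Can both statements be true at SD 2.6?** Yes, and in more than one way.
- *Concentrated benefit:* 25% of patients gain 4.8 points and the rest nothing; 0.25 × 4.8 = 1.2.
- *Unequal spread:* normal changes with SD 1.48 on placebo and 3.37 on active, pooled √((1.48² + 3.37²)/2) = 2.60. The means are 4 − 0.524 × 1.48 = 3.22 and 4 + 0.126 × 3.37 = 4.42, so the difference is 1.2 with 30% and 55% response.
- *Common shift:* placebo changes of 0 (45%), 3.4 (25%) and 6 (30%). Mean 2.65, variance 13.69 − 7.02 = 6.67, SD 2.58, response 30%. Adding 1.2 to everyone moves the middle group to 4.6, and response becomes 55%.

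These are contrived, but they show that the two statements are not logically incompatible.

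**5. Unevaluable patients (assumed numbers, left out of the analysis).**

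| Evaluable per arm | Fisher, 30/55 | CMH, 30/55 | t-test, 1.2 points |
|---|---|---|---|
| 95 | 92.0% | 94.0% | 88.6% |
| 90 | 90.8% | 92.7% | 86.9% |
| 85 | 89.3% | 91.9% | 84.9% |

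If 10% of patients were instead kept and counted as non-responders, power at 30/55 would be 88.5% (Fisher) or 91.1% (CMH).

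**The case for a change.** The best case for a change is that the sponsor chose to power both measures in one paragraph, on one scale, without saying which effect it expects. At SD 2.6 every ordinary shape tried with a common 1.2-point shift left the primary test below 93%, so the direction does not hang on normality. The primary visit is fixed at Week 2; if the 1.2 points belong elsewhere, the plan could say so. The attrition point needs no distributional model, and the remedy would be only wording.

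Part of this stands. The paragraph should not be read as promising 90% or more on both measures for a single effect, and the visit, the variable behind the SD, the basis for the response rates and the evaluable number are all unstated. What does not stand is the step from there to a defect. The plan assumes 30% and 55% for the primary endpoint; it offers 1.2 points as a difference detectable on a secondary one, and nowhere calls it the expected effect of the drug. The replacement figure of 67% to 72% would itself rest on an undefined SD and a chosen distribution. Writing it into Section 1.1 would swap a figure that is correct at stated assumptions for one that is correct only at unstated ones.

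**Conclusion.** No change to the plan is needed. The stated power for the primary endpoint is correct at the response rates assumed, and so is the separate figure for the continuous score. The mismatch, 1.69 against 1.2 points with primary power of 67% to 72%, is sound arithmetic only if change is roughly normal, 2.6 is the SD of Week 2 change and placebo response is 30%. Across the shapes tried at SD 2.6 the Fisher range is 63% to 90%, and a smaller SD of change narrows or removes the gap. The missing details are ones that the sponsor's statistician can supply on request. Supplying them would leave the 200 patients, the CMH test and the conclusion drawn from the result as they are. The allowance for unevaluable patients is a small matter: at an assumed 10% excluded, the planned CMH test still has 92.7% power at the plan's own rates, close to the 93% quoted, because the Fisher calculation is the more conservative of the two. The t-test figure does slip to 86.9%, but it supports a secondary outcome.

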1.2. Statistical Methods and Analysis Plan

This section describes the planned statistical analyses in general terms. A complete description of the methodology will be specified in a statistical analysis plan (SAP). Any changes in the statistical methods described in this protocol that occur prior to database lock will be documented in the SAP and will not require a protocol amendment.

